9. DATA ANALYSIS

Study Hypotheses: The primary objective of this study is to evaluate the reduction of itch and nighttime scratch (as measured by accelerometry/actigraphy and Observer Reported Itch Assessment (ages 3 months to \leq 11 years old) with application of crisaborole. A clinically significant change in scratching as measured by accelerometry/actigraphy has not yet been determined. The relationship between accelerometry/actigraphy scratching parameters and PRO scratching assessments is being studied currently. This study adds to the knowledge base by studying the association between changes in PRO scratching assessments and changes in accelerometry/actigraphy scratching parameters when treatment is initiated or changed. Estimates of their variability from this study can also fill the literature gap and be used to help design future studies.

As this study is a research collaborative agreement, both the Laboratory for Human Neurobiology and the collaborator/sponsor will perform statistical analyses. Only deidentified data is shared with the collaborator.

Sample Size: The sample size calculation of this study is therefore based on the primary endpoint for itch assessment. An open-label internal Pfizer study with a similar scale to the Observer Reported Itch Assessment in 3-months to 5-year olds, the reduction of itch/scratch was evaluated from baseline to 14 days. Based on the results of that study, a 2.6 points common standard deviation in the observer reported pruritus score change from baseline for 2 weeks in children ages 3 months to 5 years with mild to moderate AD was assumed. There is no data available for 6 \leq 11 year olds. Therefore, the assumption is made that children ages 6 to \leq 11 will have the same standard deviation. We will employ a simple randomized procedure using a computerized random numbers to assign participants to the two groups. A total of 244 randomized participants (in 1:1 ratio) will provide approximately 85% power to detect a 1.0 points of the observer reported pruritus score reduction difference in crisaborole treatment group compared to vehicle group, with a two-sided 5% significance.

With an expected dropout rate of ~10%, approximately 540 (270 children and 270 primary adult caregivers) are expected to be recruited for this study.

Statistical Methods and Analysis:

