The primary and secondary endpoints will be tested at the significance level of 0.05 (2-sided). There is no multiplicity adjustment. Number, percent and 95% confidence interval (CI) will be presented for binary endpoints. Descriptive summary statistics (n, Mean, Std. Dev, Median, Min., Max.) will be presented for continuous endpoints. In addition, graphics may be used to present the data.

The primary objective is to evaluate the effects of Crisaborole on itch and night-time scratch. The primary endpoints include number of scratching episodes (children aged 2 – \leq 11 years), duration of scratching (children aged 2 – \leq 11 years), and ORIA (ages 3 months to \leq 11 years). For these endpoints, change from baseline will be analyzed using a mixed-effects model with repeated measures (MMRM) including data from Day 1 (for accelerometry measured scratch episodes and duration)/Day 2 (for ORIA) to Day 15 with baseline score as a covariate and an unstructured covariance matrix. The least-squares (LS) means and

the corresponding 95% CIs, the LS mean difference between treatment groups, and the corresponding 95% CI will be presented for change from baseline for all postbaseline timepoints. As a sensitivity analysis, instead of daily data, average of every 3 days data will be used to account for day-to-day variation.

The binary endpoints will be descriptively summarized using sample size, number, percentage and 95% confidence interval (CI) of percentage at each time point. Binary data will be analyzed by comparing response rates between treatment groups. Normal approximation to the difference in response rates will be used to obtain p-values and 95% CI. For binary endpoints analyzed at each scheduled visit separately, participants who drop out for any reason or require a prohibited medication for the treatment of their atopic dermatitis will be defined as “non-responsive” at all subsequent visits. This method of handling missing response is known as missing response as non-response (MR-NR).

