Mixed model repeated measures (MMRM) will be used to analyze longitudinal continuous data. Treatment, visit, treatment-by-visit interaction are fixed effects in the model, baseline value as a covariate. Within-participant variability will be accounted for using a random effect with the unstructured covariance matrix. If this is a convergence issue, other type of covariance matrix will be used. The following structures will be executed in the order specified (essentially in decreasing order of complexity) until convergence is achieved: heterogeneous Toeplitz, heterogeneous first order autoregressive, autoregressive, heterogeneous compound symmetry, compound symmetry, and variance components. The first structure yielding convergence will be used as the primary analysis. The Kenward and Roger method for calculating the denominator degrees of freedom for tests of fixed effects will be used. Least square (LS) estimates of mean values and the LS mean differences between crisaborole 2% BID and vehicle groups at each visit will be derived from the model. The corresponding p-value, standard error (SE) and 95% CI will also be derived from the model.

ANCOVA model will be used to analyze nonlongitudinal continuous endpoints with treatment as a factor baseline value as a covariate. Least square (LS) estimates of mean values and the LS mean differences between crisaborole 2% BID and vehicle groups at each visit will be derived from the model. The corresponding p-value, standard error (SE) and 95% CI will also be derived from the model.

For any accelerometry/actigraphy continuous variables that exhibit right skewed distribution (i.e. skewed to positive values), log transformation may be used as appropriate. Specifically, for number of scratching, length of time scratching, arousals from sleep, WASO, and sleep onset latency, $\log(x+1)$ transformation will be employed (to include possible zero values). For time duration between scratching, $\log(x)$ will be employed.

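### The covariance fallback list is not in its stated order: constant-variance AR(1) is tried before heterogeneous compound symmetry, so a fallback could give wrong per-visit standard errors

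*Combined protocol and SAP*

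**What the plan says.** All references are to Section 9 (Data Analysis) of the combined protocol and SAP, under Statistical Methods and Analysis.

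- The primary endpoints (number of scratching episodes, duration of scratching, ORIA) are analysed as change from baseline in a repeated-measures model, "including data from Day 1 (for accelerometry measured scratch episodes and duration)/Day 2 (for ORIA) to Day 15". Baseline is a covariate and the first-choice covariance is unstructured.
- If that does not converge, other structures are tried in a fixed sequence described as "essentially in decreasing order of complexity". Heterogeneous Toeplitz and heterogeneous first-order autoregressive come first, followed by "autoregressive, heterogeneous compound symmetry, compound symmetry, and variance components".
- "The first structure yielding convergence will be used as the primary analysis".
- Standard errors, p-values and confidence intervals come from the fitted model with Kenward-Roger degrees of freedom. No empirical (sandwich) standard error and no check of the chosen structure are mentioned.
- Treatment differences are reported at every post-baseline time point.
- Within-child variability is said to be handled by a random effect, which leaves open whether the listed structures describe the residual matrix.

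**The concern.** The order matters because the rule is automatic: whatever converges first is the primary result. As written, the sequence drops to a 2-parameter constant-variance model and then climbs back to a heterogeneous one. A model that forces one variance on all days uses a pooled SD for every per-visit difference. If the variance of change grows during treatment, the Day 15 standard error is then too small, which raises the false-positive rate. The early standard errors are too large, which costs power where the study's stated interest in rapid onset lies. Kenward-Roger works within the chosen structure and does not correct a wrong one.

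A fallback is plausible. At 14 or 15 daily time points the unstructured matrix has 105 or 120 parameters, and the scratch endpoints use only children aged 2 to 11.

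**Working it through.** **1. The plan's own figure.** Inputs: difference 1.0 and 85% power ("A total of 244 randomized participants (in 1:1 ratio) will provide approximately 85% power to detect a 1.0 points"), SD 2.6 ("a 2.6 points common standard deviation in the observer reported pruritus score change from baseline for 2 weeks"), and two-sided 5%. Per arm, n = 2 × 2.6² × (1.960 + 1.036)² / 1.0² ≈ 121.4, so 122 per arm and 244 in total. Power at 122 per arm is 0.852. Allowing for 10% dropout gives 269 to 272 depending on the formula, against about 270 planned. The sample size reproduces and is not affected by this point.

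**2. Parameter counts in the listed order.** With T repeated days, T = 14 for ORIA (Day 2 to 15) and T = 15 for scratch (Day 1 to 15):

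| Structure | Formula | T = 14 | T = 15 |
|---|---|---|---|
| Unstructured | T(T+1)/2 | 105 | 120 |
| Heterogeneous Toeplitz | 2T − 1 | 27 | 29 |
| Heterogeneous AR(1) | T + 1 | 15 | 16 |
| AR(1) | 2 | 2 | 2 |
| Heterogeneous CS | T + 1 | 15 | 16 |
| CS | 2 | 2 | 2 |
| Variance components (as residual structure) | 1 | 1 | 1 |

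The count rises from 2 to 15 or 16 between AR(1) and heterogeneous CS.

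**3. Effect on per-visit standard errors if the rule stops at AR(1).** Assumptions: complete data, ORIA on the raw change scale, and SD of change rising linearly over 14 days from s at Day 2 to 2.6 at Day 15. The documents give only the 2.6; s is assumed. The constant-variance fit uses approximately the pooled SD, the square root of the mean of the 14 daily variances. The ratio of model to true standard error on a given day is pooled SD / true SD, and the true type I error is 2 × [1 − Φ(1.96 × ratio)].

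| s | Pooled SD | Ratio Day 15 | Error Day 15 | Ratio Day 2 | Error Day 2 |
|---|---|---|---|---|---|
| 2.6 | 2.60 | 1.00 | 5.0% | 1.00 | 5.0% |
| 2.3 | 2.45 | 0.94 | 6.5% | 1.07 | 3.7% |
| 2.0 | 2.31 | 0.89 | 8.2% | 1.15 | 2.4% |
| 1.5 | 2.08 | 0.80 | 11.7% | 1.39 | 0.7% |

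Example, s = 2.0: 2.31 / 2.6 = 0.888 and 1.96 × 0.888 = 1.74, giving 8.2%.

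**4. What the skipped structure would give.** The best-fitting AR(1) and heterogeneous CS matrices were compared with assumed true matrices: compound symmetry, or a compound-symmetry/AR mixture, with correlation parameter 0.3 to 0.7. The SD was either constant at 2.6 or rising from 1.3 to 2.6. Heterogeneous CS gave a Day 15 ratio of 1.00 to 1.02 throughout. With the rising SD, AR(1) gave about 0.77 (error about 13%).

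**5. Variance components.** As a residual structure this sets the within-child correlation to zero. For a single-visit difference with complete data and constant SD, the ratio is 1.00, so there is no distortion. For a 14-day average with within-child correlation ρ, the standard error is understated by √(1 + 13ρ): 2.2, 2.7 and 3.2 times for ρ = 0.3, 0.5 and 0.7 (assumed).

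**The case against.** The case for leaving the list alone has real substance.

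- The list is fully pre-specified, so there is no post hoc choice. It is hedged by the word for approximately, and it runs by family, heterogeneous before homogeneous within each. This stands as an explanation of how the list arose. It does not make the description correct: a rise from 2 to 15 or 16 parameters is not a near-tie.
- AR(1) is reached only after the unstructured matrix and two heterogeneous structures fail. If the separate daily variances caused those failures, heterogeneous CS, with as many parameters as heterogeneous AR(1), may fail too. This stands: reordering may not always help. It costs nothing to try.
- The variance path is assumed. Nothing in the documents shows that the SD rises, and with a constant SD the Day 15 error is 5%. The SD used is that of raw change, whereas the model adjusts for baseline. This stands and is why a range is given.

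Stronger readings are tempting but not supported:

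- A reader might infer that the primary standard errors could be wrong by a factor of 2 to 3. That size belongs to a day-averaged contrast, which the plan does not specify, and to a last step reached only after five fallbacks fail, two of them (AR(1) and CS) with only 2 parameters.
- A reader might take the last step to be independence for certain. If variance components means a random intercept, which the random-effect wording allows, it equals compound symmetry.
- A reader might apply the 8% to 12% to all three primary endpoints. The two scratch endpoints are analysed as log(x+1), and the documents offer no variance path for them.

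**Conclusion.** The point holds as a minor, conditional defect in the specification. The list contradicts its own ordering principle, and the rule can fix a constant-variance model as primary while a heterogeneous one is untried. If that happens, the true type I error for the ORIA difference at Day 15 lies between about 5% (constant SD) and 12% (SD rising from 1.5), with a correspondingly conservative test at Day 2 (5% down to 0.7%). These figures rest on an assumed linear SD path, complete data and the raw change scale. They say nothing about how likely the fallback is.

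Variance components would rarely be reached. If it is the residual structure, its harm lies elsewhere than in single-visit standard errors under constant variance. It stops the model using a child's earlier values, which weakens the missing-at-random handling that Section 9 relies on, and it would badly understate the standard error of any day-averaged effect.

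**What to change.** Amend the SAP text before unblinding:

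1. Order the fallbacks as heterogeneous Toeplitz, heterogeneous AR(1), heterogeneous CS, AR(1), CS.
2. Delete variance components.
3. State that the structures apply to the residual (within-child) matrix, and remove or clarify the random-effect wording.
4. Whenever the fitted structure is not unstructured, use empirical (sandwich) standard errors with a named, compatible degrees-of-freedom method.

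The cost is wording only, with no new data, visits or children. Kenward-Roger is given up in the fallback fits. The scratch analyses cover ages 2 to 11 only and so have fewer than about 120 children per arm, which makes a small-sample sandwich correction advisable there. Sandwich errors correct the standard error. They do not repair a point estimate that depends on the covariance model when data are missing at random, which is a further reason to try the richer structures first.

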10. DATA HANDLING, RECORD KEEPING, QUALITY CONTROL AND QUALITY ASSURANCE

Data handling, record keeping, quality control and quality assurance is discussed in the approved Boston University Institutional Review Board (IRB) application.

10.1 Confidentiality

In order to minimize the accidental release of sensitive test information, study data will be labeled with only the participant's randomly generated study ID. To protect the confidentiality of each participant, the only place where the participant ID and their identifiable information will exist together will be on a separate master spreadsheet, which will be password protected and to which the PI and the study coordinator will have access to. In order to further ensure the confidentiality of the participants, the password for this master spreadsheet will be different than the password for documents containing the de-identified data. We will use a coded ID number on all results and data acquired and stored.

Only the consent form, screening forms, BuildClinical recruitment database, and the master identifier spreadsheet will contain identifiable information. Consent and screening forms will be locked in a cabinet at the Spivack Center. All electronic data will be stored in password-protected computers located in a secure lab space in the Spivack Center. Data being stored electronically will be stored according to BU policy for the secure storage of such data.

No identifiable data will go anywhere outside of BU. All data transferred will be coded with no direct identifiers with a unique study ID.

The master identifier spreadsheet will be kept past the end of the study for a minimum of 7 years after which point it will be securely deleted (electronic) or shredded (paper forms). Only the Principal Investigator and study coordinator will have access to this data. Publications will not contain the participants' names or any identifying characteristics

The study monitor or other authorized representatives of the sponsor may inspect all deidentified documents and records required to be maintained by the investigator, including but not limited to pharmacy records, for the participants in this study. The clinical study site will permit access to such records.

A description of this clinical trial will be available on <http://www.ClinicalTrials.gov>, as required by U.S. Law. This website will not include information that can identify participants. The website may be updated to include a summary of the results.

10.2 Data handling, data collection and extract transform and load (etl) processes

Electronic Data Capture: Both a web-based electronic data capture (EDC) system and computing applications (apps) on a mobile device will be utilized for this study, in addition to sensor data.

Source Documents: Study visit data (e.g., screening, demographics, medical history, ISGA, EASI, BSA, vitals, concomitant medications, and inclusion exclusion criteria) will be collected for all screened and enrolled participants and entered into Excel CSV files for transfer via CONFORM to Pfizer.

Sensor-acquired data (Actigraphy/accelerometry devices) will include no identifiable information and will be exported from each sensor device via each device's proprietary companion software application. Data obtained from the watches will be transferred to Pfizer for processing via a cloud-based data repository, CONFORM, and the results will then be subsequently shared back with BU via CONFORM.

Data dictionary will be aligned to CDISC and Pfizer Standards. Device type, manufacturer, serial number, firmware and software versioning will also be collected as well as all the pertinent metadata associated with the generated files.

Data generated by the methods described in the protocol will be recorded in the participants' study records and/or study progress notes. Data may be transcribed legibly on study records for each participant or directly inputted into an electronic system or any combination thereof.

BuildClinical Recruitment Database: The BuildClinical online database for participant recruitment will be maintained until the end of the study.

10.3 Participant Study Records and Report Forms

The participant study records and report forms will be the primary data collection instrument for the study. All data requested on the participant records will be recorded. All missing data will be explained. If a space on the participant records is left blank because the procedure was not done or the question was not asked, "NaN" will be written. If the item is not applicable to the individual case, "N/A" will be written. All entries will be printed legibly in black ink. If any entry error has been made, to correct such an error, a single straight line will be drawn through the incorrect entry and the correct data will be entered above it. All such changes will be initialed and dated. There will be no erasures or white-out on participant records. For clarification of illegible or uncertain entries, the clarification will be printed above the item, then initialed and dated.

10.4 Study Records Retention

Data from the intake of eligible participants will be retained in a locked file cabinet. The investigators will maintain a password-protected list containing the names and contact information of those individuals who are ineligible. All files will be destroyed 7 years after study completion. Only approved researchers will have access to these files. Answers to screening questions will be destroyed for both persons who are eligible and persons who are not eligible. The only information that will be retained from persons who were screened will be contact information and general reason for screening out (for those who are not eligible). The BuildClinical database for participant recruitment will be maintained until the end of the study. All potential participants who respond to BuildClinical recruitment materials will be contacted by study staff to verify eligibility via the Phone Screening Questionnaire. The only information that will be retained from persons who were screened will be contact information and general reason for screening out (for those who are not eligible).

The BMC/BU Medical Campus IRB requires that documentation of informed consent of participants be retained for at least seven years after the study is closed. Such records will be preserved in hardcopy and/or electronic or other media form and must be accessible for inspection and copying by authorized individuals.

11. COMPLIANCE WITH GOOD CLINICAL PRACTICE

11.1. Ethical Conduct of the Study

The study will be conducted in accordance with the Declaration of Helsinki on Ethical Principles for Medical Research Involving Human Participants, adopted by the General Assembly of the World Medical Association (2008).

In addition, the study will be conducted in accordance with the protocol, the principles of the International Conference on Harmonization (ICH) guideline on Good Clinical Practice (GCP) and applicable local regulatory requirements and laws.

11.2. Institutional Review Board (IRB)/Ethics Committee (EC)

It is the responsibility of the investigator to have prospective approval of the study protocol, protocol amendments, informed consent documents, and other relevant documents, e.g. advertisements, if applicable, from the IRB/EC. All correspondence with the IRB/EC should be retained in the investigator file.

This protocol and any amendments will be submitted to the Boston Medical Center and Boston University Medical Campus IRB, for formal approval of the study conduct. The decision of the IRB concerning the conduct of the study will be made in writing to the investigator. A copy of the initial IRB approval letter will be provided to the sponsor before commencement of this study.

The only circumstance in which an amendment may be initiated prior to IRB/EC approval is where the change is necessary to eliminate apparent immediate hazards to the participants. In that event, the investigator must notify the IRB/EC in writing within 5 working days after the implementation.

11.3. Participant Information and Consent

All participants for this study will be provided a consent form describing this study and providing sufficient information for participants to make an informed decision about their participation in this study. The consent form will be submitted with the protocol for review and approval by the IRB. The consent of a participant, using the IRB-approved consent form, must be obtained before that participant is submitted to any study procedure. Consent will be documented as required by the IRB.

All parties will ensure protection of participant personal data and will not include participant names or other identifiable data in any reports, publications, or other disclosures, except where required by law.

When study data is compiled for transfer to other authorized parties, participant names, addresses, and other identifiable data will be replaced by a numerical code in order to anonymize study participants. The study site will maintain a confidential list of participants who participated in the study linking their numerical code to the participant's actual identity. In case of data transfer, all parties will maintain high standards of confidentiality and protection of participant personal data consistent with applicable privacy laws.

The informed consent and assent documents must be in compliance with ICH GCP, local regulatory requirements, and legal requirements, including applicable privacy laws. The investigator will ensure that each study participant and his or her parent(s)/legal guardian are fully informed about the nature and objectives of the study and possible risks associated with participation. The informed consent and assent documents used during the informed consent process must be reviewed by the sponsor, approved by the IRB/EC before use, and available for inspection. The investigator must ensure that each study participant is fully informed about the nature and objectives of the study and possible risks associated with participation.

The investigator, or a person designated by the investigator, will obtain written informed consent from each participant's legal guardian before any study-specific activity is performed, unless a waiver of

informed consent has been granted by an IRB/EC. The investigator will retain the original of each participant's guardian(s) signed consent document.

The informed consent document used during the informed consent process will convey that only anonymized information (including protected health information related to age, and sex) from each participant may be conveyed to Pfizer and its third parties/affiliates.

